There are 3 distinct projects within this follow-up study, the aims and objectives have been divided by project to clearly demonstrate how they will be implemented:

Project 1:

The aim of project 1 is to refine our estimates of diagnostic accuracy of MR imaging as a technology to aid the prenatal diagnosis of fetal developmental brain abnormalities.

- 1) We will reassess the diagnostic accuracy of MR imaging compared to antenatal US through:
 - a) Measurement of diagnostic accuracy of antenatal US alone (i.e. prior to iuMR) relative to updated reference diagnosis at 2-3 years of age (post-natal imaging or post-mortem examination);
 - b) Measurement of diagnostic accuracy of iuMR (following antenatal US) relative to the updated reference diagnosis at 2-3 years of age (post-natal imaging or post-mortem examination).

Project 2:

The aim of project 2 is to improve the prognostic information available during pregnancy based on the functional and developmental outcomes of the MERIDIAN cohort.

- 1) We will quantify the value of prognoses based on MR imaging and on USS by:
 - a) Assessing the concordance between severe neurodevelopmental impairment (defined by BSID score of <80 on the Cognitive AND language index or a combined score of <85 or a motor score of <70, evidence of severe disability based on a score <-2SDs for the ASQ, or evidence of cerebral palsy based on GMFCS) and poor prognosis, based on MR and on USS;
 - b) Comparing the relative prognostic accuracy of USS and MR imaging;
- 2) We will qualitatively assess the cases for which the USS prognosis and MR prognosis differed, in relation specifically to the original diagnoses;
- 3) We will look at the concordance in the subgroup of children for which the MR scan was performed within 24 weeks;
- 4) We will assess ability to predict non-severe impairment (defined as BSID <85 or a score between 1 and 2 SDs for the ASQ).

Project 3:

The aim of project 3 is to assess the clinical significance of isolated, mild ventriculomegaly.

- 1) We will assess the clinical significance through:
 - a) Identification of all isolated, mild ventriculomegaly cases diagnosed on in utero MR in the MERIDIAN cohort and define their developmental outcome at 2-3 years (as per project 2);
 - b) Comparison of developmental outcome to the prognoses made based on USS.

3. Study design

Multi-centre observational cohort study of diagnostic accuracy and functional development of children born from the MERIDIAN study.

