Where it is not possible to arrange a face to face appointment, or if for any reason the questionnaires are not completed during the appointment then there will be the option for the GMFCS questions (adapted for parent completion) and SDQ to be posted out or given to parents for them to complete and return to the research team. Alternatively the questionnaires can be completed over the telephone with the child's parent.

The research team will categorise the children as severely impaired (scoring <70), mild-moderately impaired (scoring 70-85) or normal (scoring 85+) based on the results of the developmental assessments. These categories will be used to complete the developmental assessment CRF.

After the developmental assessments all participants will be debriefed via a feedback letter from the research team, which will contain details of the results from the developmental assessment. Where an important previously unrecognised disability has been identified, we will speak to parents about future actions. Typically this would include informing the GP and advising about appropriate referrals either to community paediatrics or therapy services. A member of the study team (NE, an experienced paediatrician) would be available for discussion and advice if the best course of action was not immediately apparent.

Project 3

There is no input required from the MERIDIAN participants or research sites for completion of project 3. Project 3 will be completed by the central study team at the University of Sheffield.

[figure not shown]
The information for project 3 will come from the assessments described in project 2. We will identify all cases of isolated mild ventriculomegaly diagnosed on iuMR and define their developmental outcome at 2-3 years as severely impaired, mild-moderately impaired or normal as per project 2. In MERIDIAN, the most common information given to women on the basis of isolated mild VM on USS is "favourable (90%)" followed by poor or intermediate and the remainder as normal.

We will calculate the prevalence of severe and non-severe impairments in isolated mild VM cases.

Please see Figure 2. for details of procedures and data collection document

Figure 2. Procedure for MERIDIAN 2-3 year follow up study

Screening

Project 1 – Case note review

Project 1 and 2 – Case note review and BSID

Project 1
If consented to project 1 only research midwife will conduct medical case note review and record details of any further follow up

Project 1 and 2

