- b. Measurement of diagnostic accuracy of in utero MR (following antenatal US) relative to the updated reference diagnosis at 2-3 years of age (postnatal imaging or post-mortem examination).

Further details of methods and analyses are available in the MERIDIAN protocol [1].

The impact of non-consent to follow-up is anticipated to be very small and will not directly influence the power of the study. All MERIDIAN cases will be retained (using original diagnosis if no consent is received); meaning that the effective sample size is likely to increase where the additional follow-up yields data where previously none was available.

Sample size Project 1

The original MERIDIAN study requires data on 336 children to detect a 10% improvement in diagnostic accuracy. We anticipate the number of participants consenting to repeat examination will be much greater than 336, and the improvement in diagnostic accuracy to be greater still than 10% due to better quality reference data.

Analysis of Project 2

Results from the BSID will allow us to determine the developmental outcome and categorise as; severely impaired, mild-moderately impaired or normal. For the purpose of this analysis, we will consider a severely impaired neuro-developmental outcome as being one where:

- i) The BSID psychomotor component is below 70 (physical impairment)
- ii) The BSID score of <80 on the Cognitive AND language index
- iii) The cognitive and language index has a combined score of <85
- iv) Cerebral palsy on GMFCS
- v) Where there was no BSID assessment, but where the ASQ is <2 SDS below the mean corrected for age

The primary analyses will focus on this as a dichotomous outcome (severe impairment: yes/no). Secondary analyses will further assess whether the prognoses also differentiate children with a BSID of between 70 and 85 (which we tentatively term "mild to moderate impairment") from those with unequivocally normal development (85 or above). We will also assess the actual range of scores within each prognostic category.

There are two primary (and sequential) considerations:

- 1) To quantify the value of prognoses based on MR and on USS
- 2) To assess whether the prognostic value of MR increases relative to that of USS

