The first consideration is a pre-cursor to the second, since the comparison in 2) is irrelevant if neither MR nor USS contain some measure of useful prognostic information. We will quantify 1) by assessing the concordance between severe neurodevelopmental impairment (BSID score of <80 on the Cognitive AND language index or a combined score of <85 or a motor score of <70) and poor prognosis, based on i) MR and ii) USS. The sensitivity, specificity, positive and negative predictive values of MR and of USS will be reported.

The second consideration is to compare the relative prognostic accuracy of USS and MR. We will do so by calculating the difference in the respective sensitivities and specificities using the paired sample methods recommended by Newcombe [18].

	Outcome	
	Severe impairment (BSID<70) N=xxx	No severe impairment (BSID>=70) N=xxx
USS prognosis		
Poor	n (%)	n (%)
Normal/favourable	n (%)	n (%)
% correctly classified*	$P_{sens (USS)}$	$P_{spec (USS)}$
MR prognosis		
Poor	n (%)	n (%)
Normal/favourable	n (%)	n (%)
% correctly classified*	$P_{sens (MR)}$	$P_{spec (MR)}$
Difference (95% CI)	$P_{sens (MR)} - P_{sens (USS)}$	$P_{spec (MR)} - P_{spec (USS)}$
P-value (McNemar)		

* Here, we consider "Correct" to mean 1) Poor prognosis corresponds to severe impairment, and 2) Normal/favourable prognoses correspond to no severe impairment. The percentages correctly classified reflect 1) sensitivity and 2) specificity respectively.

The secondary outcomes are

- 3) To assess qualitatively the cases for which the USS prognosis and MR prognosis differed, in relation specifically to the original diagnoses
- 4) To look at the concordance in the subgroup of children for which the MR scan was performed within 24 weeks
- 5) To assess ability to predict non-severe impairment

The last of these will further subdivide children without severe impairment (BSID>=70) into "mild-moderate impairment" (BSID between 70 and 85) and "Normal" (BSID>85). The corresponding prognostic categories are "Intermediate" and "Normal or Favourable", and the concordance between the three prognostic categories and the three outcomes will be reported by two-way tabulations.

Sample size Project 2

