Appendix 1 - Developmental assessments

A full assessment will require determination of developmental, sensory, psychomotor and behavioural functioning. We propose to use validated parent completed questionnaires (GMFCS and SDQ) [16-17] where it is not possible to arrange a face to face assessment in order to minimise loss to follow up. These can also be completed via telephone if paper copies are not returned. This is an important and pragmatic approach because it allows us to minimise loss to follow up, whilst robustly determining the true proportion of children with a severe impairment. A face to face assessment will take between 1 and 2 hours and will be completed by a suitably trained paediatrician, physiotherapist or other health professional, and will include:

- BSID III [15] – mental and psychomotor developmental index; time 30-60 minutes.
- Motor function – BSID III and GMFCS [16]; time 5 minutes
- Sensory impairment – parent reported use of hearing or visual aids: time <5 minutes
- Behaviour – SDQ [17] a brief behavioural screening questionnaire which consists of 25 questions

The primary outcomes will be based on BSID III [15], supplemented where necessary by the ASQ [14], and give the proportion of infants surviving without mild, moderate or severe disability at 3 years. This data will be supplemented by using validated questionnaires (GMFCS and SDQ) [16-17] comprising forced-choice items to assess sensory impairment and standardised measures to assess motor and cognitive function and to identify children with:

- Mild/moderate/severe vision or hearing impairment
- Any motor impairment (cerebral palsy with GMFCS level 2)/severe motor impairment (cerebral palsy with GMFCS level 3, 4 or 5)
- Moderate/severe cognitive impairment will also be assessed using ASQ [14] which is a well validated widely used tool appropriate for children at this age, and is easily completed by parents.

Definitions for motor and sensory impairments described above are as defined by British Association of Perinatal Medicine (BAPM 2008).

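### The follow-up study's primary outcome, severe impairment, is defined by a composite rule in the text but by a BSID cut-off of 70 in the primary table and CRF categories, and the two classify some children differently

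*Protocol*

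**What the plan says.** All references are to the 2-3 year follow-up protocol.

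- **Section 2, Project 2 aims.** The BSID part of severe impairment is "BSID score of <80 on the Cognitive AND language index or a combined score of <85 or a motor score of <70". The aims add an ASQ criterion, "evidence of severe disability based on a score <-2SDs for the ASQ", and cerebral palsy on the GMFCS. A later aim concerns "non-severe impairment (defined as BSID <85 or a score between 1 and 2 SDs for the ASQ".
- **Section 6, Project 2.** The research team sorts children into categories for the CRF: "severely impaired (scoring <70), mild-moderately impaired (scoring 70-85) or normal (scoring 85" and above). It does not say which BSID score is meant.
- **Section 7, Analysis of Project 2, items i to v.** Severe means psychomotor below 70, cognitive and language both below 80, "The cognitive and language index has a combined score of <85", cerebral palsy on the GMFCS, or, as item v, "Where there was no BSID assessment, but where the ASQ is <2 SDS below the mean corrected for age". The primary analysis uses this dichotomy. The next sentences describe a BSID of 70 to 85 as mild to moderate.
- **Section 7, text before the table.** Only the three BSID criteria are repeated.
- **Section 7, primary table.** The columns are "Severe impairment (BSID<70) N=xxx" and its complement, BSID of 70 or more. The rows are poor and normal/favourable prognosis.
- **Section 7, Sample size Project 2.** Non-survivors have no BSID but enter the primary analysis as poor outcomes.
- **Appendix 1.** Motor function is graded, with "severe motor impairment (cerebral palsy with GMFCS level 3, 4 or 5") as the severe grade.

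**The concern.** The composite rule and the cut-off of 70 are both stated as the definition of one primary outcome, and neither contains the other. Some children are severe under the rule although every score is 70 or more. Others have a score below 70 and are not severe under the rule.

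The primary table reports sensitivity within the severe column and specificity within the other, with a McNemar test in each. Moving children between columns changes both denominators and both tests. Project 3 reuses the same categories for its prevalence estimate. If the choice is left open until the data are seen, the primary result can depend on which version the analyst picks.

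This is not detail left to an SAP, because the protocol states both definitions.

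**Working it through.** **Step 1. Apply both definitions to example children.** Scores are cognitive / language / motor. *Combined* is taken as the mean of cognitive and language, since the protocol does not define it.

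| Scores | Combined | Section 7 rule | Cut-off of 70 (table, CRF) |
|---|---|---|---|
| 84 / 84 / 100 | 84 | severe (iii) | not severe, 70-85 band on cognition and language |
| 78 / 78 / 90 | 78 | severe (ii and iii) | not severe, 70-85 band on cognition and language |
| 90 / 90 / 90 with cerebral palsy | 90 | severe (iv) | not severe, normal |
| 65 / 110 / 100 | 87.5 | not severe | one score below 70 |

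The conflict does not hang on the meaning of *combined*. The second child is severe by item ii and the third by item iv, whatever it means. The meaning still matters. Read as the mean, item iii absorbs item ii, because two scores below 80 average below 80 and so below 85. Read as a sum, item iii would need the two indices to average below 85/2 = 42.5.

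**Step 2. Other wording that does not line up.**

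- ASQ: section 2 says below minus 2 SD. Item v, read literally, says less than 2 SD below the mean.
- Cerebral palsy: item iv gives no GMFCS level, while Appendix 1 grades motor impairment by level.
- Non-severe impairment in section 2 is BSID below 85 with no lower bound, so it also takes in scores below 70.
- A score of exactly 85 is in both the middle and the normal band in section 6. It is normal in section 7's secondary analysis (85 or above) and not normal in its three-way split (above 85).
- The primary table has no row for Intermediate prognosis, and its BSID-labelled columns do not say where non-survivors go.

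**Step 3. Illustrative size.** The plan gives no figure for the proportion severe, so there is nothing to reproduce. Assumptions, none from the documents: the three scores are trivariate normal with SD 15, common mean 100 or 85, common correlation r from 0.4 to 0.8, and *combined* is the mean. Only the BSID criteria (i to iii) are counted.

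The SD of the mean of two indices is 15 × √((1 + r)/2), which is 12.55 at r = 0.4 and 14.23 at r = 0.8. At mean 100:

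- P(combined < 85) = Φ(−15/12.55) = 11.6%, and Φ(−15/14.23) = 14.6%.
- P(one scale < 70) = Φ(−2) = 2.3%.

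Simulation of the whole rule:

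| Mean, r | Rule i-iii | Any scale < 70 | Mean cognitive-language < 70, or motor < 70 |
|---|---|---|---|
| 100, 0.4 | 12.8% | 6.0% | 3.0% |
| 100, 0.8 | 14.7% | 4.5% | 3.1% |
| 85, 0.4 | 53.4% | 34.0% | 22.6% |
| 85, 0.8 | 50.3% | 25.8% | 20.5% |

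Ratios at mean 100 run from 12.8/6.0 = 2.1 to 14.7/3.1 = 4.7. At mean 85 they run from 53.4/34.0 = 1.6 to 50.3/20.5 = 2.5.

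**Step 4. Dilution by non-survivors.** Suppose 400 scored children at mean 100 and r = 0.4. The rule gives 0.128 × 400 = 51 severe, and any scale below 70 gives 0.060 × 400 = 24. Adding 50 non-survivors to each gives 101 against 74, a ratio of 1.4.

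**Step 5. Power.** The stated 90% for 400 cases (gains of 20 points in sensitivity and 10 in specificity, two-sided 5%) can be neither reproduced nor refuted, because the number of severe cases and the discordant proportion ψ are not given. For McNemar's test, n = (1.960√ψ + 1.282√(ψ − d²))²/d². With d = 0.20 and ψ from 0.2 to 0.5, about 49 to 128 severe cases are needed. With d = 0.10 and ψ from 0.1 to 0.5, about 101 to 522 non-severe cases are needed. Power therefore depends on the column sizes, and so on the definition.

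**The case against.** The best defence is that section 7 names its operative rule: it introduces items i to v as the definition for this analysis and says the primary analysis uses that dichotomy. The BSID criteria are the same in section 2, in items i to iii and in the text before the table. The mild-to-moderate label is secondary and tentative, and the later split applies only to children without severe impairment. The table headers and CRF bands may simply have been missed when section 7's BSID scores were updated for BSID III, as the list of changes records. This is a fair account of the likely intent. It does not remove the conflict, because the same section keeps 70-85 as a lesser category and heads its primary table with 70.

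Several stronger readings are tempting, and the documents do not support them.

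- **That the table cannot be filled.** It can be filled under either definition, but not uniquely as labelled.
- **That the ASQ rule is reversed.** Only item v's literal wording is. Section 2 shows the intent, and item v applies only where there is no BSID.
- **That the GMFCS passages contradict each other.** Appendix 1 grades motor impairment as supplementary data, whereas item iv is one criterion for overall severity. The missing level is an ambiguity.
- **That the severe group differs 5- to 6-fold.** That sets one scale below 70 (2.3%) against a two-scale mean below 85 (11.6-14.6%). Neither is the full severe column.
- **That Project 3's working prevalence below 10% is contradicted.** That rests on assumed norms and an assumed meaning of *combined*. The effect on precision would also be small: with 140 cases the standard error is √(0.10 × 0.90/140) = 2.5% at 10% and √(0.146 × 0.854/140) = 3.0% at 14.6%.

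**Conclusion.** The point stands: the Project 2 primary outcome has two stated definitions that classify some children differently. That much follows from the text, with no distributional assumption.

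The size is illustrative. Under the assumptions in the working, the composite rule labels about 13-15% severe at mean 100, against 5-6% or about 3% under two readings of the cut-off of 70. At mean 85 it labels about 50-53%, against 26-34% or 20-23%. The ratio is thus roughly 2- to 5-fold at mean 100 and 1.6- to 2.5-fold at mean 85, and smaller once non-survivors are added. The cohort's true mean is unknown.

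The ASQ, GMFCS, lower-bound and score-of-85 points are secondary wording faults to correct at the same time. Which cut-off is right is for the sponsor and is not judged here.

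**What to change.** - Reconcile sections 2, 6 and 7 and Appendix 1 to one mutually exclusive three-level definition, chosen by the sponsor and fixed before analysis. Use it in the rule, the CRF categories and the table headers.
- Define *combined*, name the BSID score behind each cut-off, and assign a score of exactly 85 to one category.
- Align item v with the ASQ wording in section 2, and state whether a GMFCS level applies to item iv.
- Say which column non-survivors enter and how Intermediate prognoses are handled in the primary table.
- Record the composite scores and derive the category centrally. Report the other stated definition as a sensitivity analysis.
- Check that the Project 2 power statement and the Project 3 prevalence assumption refer to the definition chosen.

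The cost is protocol wording, revised table headers and a derived variable. Section 7 already plans to examine the range of actual scores, so no new assessment of any child is needed.

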Our sample size is constrained by the original MERIDIAN cohort, but our data collected to date provides some assurance that we will have adequate power to address the primary outcome defined by this project. As well as approaching all children known to have survived (expected number approximately 500), our analysis will include non-surviving infants (defined as having had poor outcomes; expected number approximately 50-100). Allowing for attrition in the surviving child group we approximate that there will be 400 cases, from data collected in the entire cohort, there are almost 200 instances where prognosis changed as a result of MR imaging, of whom 38 are now classified as the poorest prognosis. Scaling these prevalence's down, 400 cases will have a 90% power to detect a 20% increase in the sensitivity and a 10% increase in specificity using the tests outlined above at a two-sided significance level of 5%.

We will quantify the impact of selective participant retention by comparing prognoses and diagnoses of consenting participants with those who refused. Non-surviving fetuses or children will by definition have no BSID outcome data, but will be included in the primary analyses as having poor outcomes. Outcomes among fetuses for whom TOP was performed are controversial, but some diagnoses (for example TOP for anencephaly) are inevitably fatal. For these cases we will use our existing independent expert panels to adjudicate whether, and how, the data should be included.

Hypothesis

The clinical significance of fetal brain abnormalities are more accurately predicted by MR imaging when compared with USS. Specifically, we predict a 10% improvement in prognostic accuracy by using MR imaging.

Analysis of Project 3

Using the categories detailed in project 2 (severely impaired, mild-moderately impaired and normal) we will calculate the prevalence of severe and non-severe impairments from our data, together with exact binomial confidence intervals and compare this to the prognoses obtained from cases where USS identified isolated mild VM. Where prognosis changed as a result of MR imaging we will assess whether this was attributable to the MR identifying further diagnoses.

Sample size Project 3

With approximately 140 cases and assuming the prevalence of poor outcome is indeed less than 10%, we will be able to estimate the prevalence to within a standard error of 2.5%.

Hypothesis

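### The follow-up protocol counts cerebral palsy at any GMFCS level as severe in its Project 2 outcome list, reserves severe for levels 3 to 5 in Appendix 1, and omits it from the concordance analysis and table

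*Protocol*

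**What the plan says.** All places are in the 2-3 year follow-up protocol.

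- **Section 2, Aims and Objectives, Project 2.** The definition of severe neurodevelopmental impairment ends with "or evidence of cerebral palsy based on GMFCS". It is joined to the other criteria by *or*, and no level is given.
- **Section 7, Analysis of Project 2, numbered list.** The fourth criterion is "iv) Cerebral palsy on GMFCS", again without a level. After the list the protocol states: "The primary analyses will focus on this as a dichotomous outcome (severe impairment: yes/no".
- **Section 7, concordance analysis.** Severe impairment is restated as "BSID score of <80 on the Cognitive AND language index or a combined score of <85 or a motor score of <70". Cerebral palsy is absent.
- **Section 7, table shell.** The outcome column is headed "Severe impairment (BSID<70) N=xxx". Cerebral palsy is again absent.
- **Appendix 1, Developmental assessments.** Motor outcome is graded as "Any motor impairment (cerebral palsy with GMFCS level 2)/severe motor impairment (cerebral palsy with GMFCS level 3, 4 or 5". Level 1 is not mentioned.
- **Section 7, sample size for Project 2.** The protocol states that "400 cases will have a 90% power to detect a 20% increase in the sensitivity and a 10% increase in specificity".
- **Section 7, Analysis of Project 3.** The Project 2 categories are reused to estimate the prevalence of severe and non-severe impairment in isolated mild ventriculomegaly.

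**The concern.** The severe/not severe split decides which denominator a child enters. Severe children form the sensitivity denominator and all others the specificity denominator. Under the table's footnote, a poor prognosis is correct only for a severe child, and a normal or favourable prognosis only for a child who is not severe. A rule that classes the same child differently from place to place therefore changes both the denominator and whether the prenatal prognosis is scored right or wrong.

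The cerebral palsy criterion is such a rule. Read from the numbered list, any level suffices. Read from Appendix 1, level 2 does not. Read from the concordance text or the table, cerebral palsy plays no part. The primary outcome of Project 2 and the prevalence in Project 3 both depend on the reading taken. Settling the BSID cut-offs or the ASQ wording would not by itself supply the missing GMFCS level.

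**Working it through.** **Step 1: test records.** Child A has cerebral palsy at level 2, BSID motor 90, cognitive and language 100, and meets no ASQ criterion. Child B is the same at level 1. Child C has cerebral palsy at level 4 and no BSID; Section 6 foresees that a BSID will not be possible in some children with complex impairments.

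| Source | Child A (level 2) | Child B (level 1) | Child C (level 4, no BSID) |
|---|---|---|---|
| Section 2; Section 7 numbered list | severe | severe | severe |
| Section 7 concordance text and table | not severe | not severe | cannot be placed |
| Appendix 1 motor grading | not severe | not placed | severe |

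The direct conflict between the numbered list and Appendix 1 is at level 2. At level 1 Appendix 1 is silent. The BSID-only versions disagree with the list at both levels.

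**Step 2: effect on scoring.** Give Child A a normal or favourable prognosis on both modalities. Under Section 2 and the numbered list the child is a sensitivity failure for both. Under the concordance text, the table or Appendix 1 the child is a specificity success for both.

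**Step 3: effect on the MR versus ultrasound comparison.** Suppose, as an assumption, 100 severe cases without such children, with MR sensitivity 70% and ultrasound sensitivity 50%. This is the 20-point gain used in the sample size. Add k children whom both modalities called normal or favourable:

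- MR sensitivity = 70/(100 + k); ultrasound sensitivity = 50/(100 + k); difference = 20/(100 + k).
- k = 5: 66.7%, 47.6%, difference 19.0 points.
- k = 15: 60.9%, 43.5%, difference 17.4 points.

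The added children are concordant pairs. The discordant counts in the sensitivity McNemar test do not change; both sensitivities fall and their difference shrinks. If the modalities disagreed on such a child, the discordant pair would move from one comparison to the other. The protocol does not say how often that would happen.

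**Step 4: the stated power.** The paired formula is n = [1.96√ψ + 1.2816√(ψ − d²)]²/d², where ψ is the discordant proportion and d the difference.

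- Sensitivity, d = 0.20: 49 severe cases at ψ = 0.20, 75 at 0.30, 101 at 0.40.
- Specificity, d = 0.10: 101 non-severe cases at ψ = 0.10, 206 at 0.20, 312 at 0.30.

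The protocol gives neither the number of severe cases nor ψ within each group, so the 90% cannot be reproduced uniquely. Assume ψ = 200/832 = 0.24 in both groups, from the almost 200 prognosis changes among the 832 participants scanned. Then 400 cases give, for sensitivity and specificity respectively:

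- 40 severe: about 75% and 98%.
- 60 severe: about 91% and 97%.
- 80 severe: about 97% and 96%.

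The stated power is attainable. For sensitivity it depends on the size of the severe group, which the definition fixes.

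**Step 5: Project 3.** With about 140 cases, one reclassified child moves the prevalence by 1/140 = 0.7 percentage points, and four move it by 4/140 = 2.9 points. The planned standard error is 2.5 points; at 10% prevalence, √(0.10 × 0.90/140) = 2.5%, which reproduces the protocol's figure.

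**The case against.** The strongest reply is that the passages describe different things. Section 7 introduces its list as a definition made for this analysis, and Section 2 matches it. Appendix 1 grades one domain, motor function, as supplementary information, and says that the primary outcomes rest on the BSID. Counting any cerebral palsy as a severe composite outcome could be deliberate.

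That stands in part: the protocol does not show that the list is the mistaken side. It does not remove the conflict. The cerebral palsy criterion is the motor limb taken from the GMFCS, Appendix 1 is the only grading of that limb, and nothing says the composite departs from it on purpose. The objection also leaves the disagreement within Section 7, where the list includes cerebral palsy and the concordance text and table do not.

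The protocol provides for parent completion of the GMFCS questions where a visit is not possible, in order to limit loss to follow-up. That is a design choice and no part of this point.

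A reader might go further in four ways that the text does not support:

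- That these children certainly enter the primary analysis as severe. The concordance text and table would leave them out, so entry is itself unsettled.
- That they are mildly affected or walking. The protocol does not describe what the GMFCS levels mean.
- That Appendix 1 calls level 1 not severe. It does not place level 1.
- That levels 1 and 2 belong in the mild-moderate class. That class is defined by BSID scores only, so this would be a new rule.

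**Conclusion.** The point holds as a contradiction in the definition of a primary outcome. Cerebral palsy below level 3 with no BSID criterion met is severe under Section 2 and the Section 7 list. It is not severe under the Section 7 concordance text and table. At level 2 it is also outside what Appendix 1 calls severe. This is a conflict between stated rules, not detail left for an analysis plan.

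Its size cannot be established. The protocol gives no number of children with cerebral palsy, no split by level and no prognoses for them. The sensitivity figures in the working illustrate the mechanism under assumed inputs and are not estimates. A reader might infer that the comparison is biased towards MR or ultrasound; that is not shown. Children called normal or favourable by both modalities lower both sensitivities and shrink the difference without altering the discordant counts. The Project 3 figure of 0.7 points per child needs only the protocol's approximate 140 cases. The matter should be corrected, and the correction is small.

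**What to change.** Use one definition of severe impairment in Section 2, the Section 7 list, the Section 7 concordance text, the table heading and Appendix 1, and state the GMFCS level in the cerebral palsy criterion. Bring the score bands in Section 6 into line.

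The choice consistent with the existing text is the threshold in Appendix 1: "severe motor impairment (cerebral palsy with GMFCS level 3, 4 or 5". If the sponsor means any cerebral palsy to count as severe, the protocol should say so and Appendix 1 should be corrected. Either way, state where levels 1 and 2 fall and whether the table includes children who are severe by the cerebral palsy criterion alone.

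The cost is a one-line change to the outcome definition, repeated wherever it appears. The GMFCS is already administered, so no new data are needed. If the Appendix 1 threshold is adopted, fewer children may be classed as severe than under the present list; the power for sensitivity should then be looked at again.
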